4.2 Study Measures

Our current usual care CDS “fires” a Best Practice Alert (BPA) for each new inpatient within the Medical Assistant (MA) check-in and vital sign workflow. The BPA requires that MAs assess tobacco use status within the past 30 days and satisfy the alert with one of three possible, mutually exclusive answers.

Intervention ordering rate is defined as the number of patients for whom any inpatient tobacco use treatment order (for medication, education, and/or TUTS counseling) was signed divided by the total number of patients in each arm for whom an order was pended and the alert fired. MAs activate “Order” tab for all patients identified as current smokers (within 30 days), resulting in placement of pended order for consult to TUT Service referral within clinical workflow.

Inpatient medication ordering rate is defined as the number of patients for whom a tobacco use treatment medication was ordered in the inpatient setting divided by the total number of patients in each arm for whom an order was pended and the alert fired.

Outpatient/discharge medication ordering rate is defined as the number of patients for whom a tobacco use treatment medication was ordered upon patient discharge from the hospital divided by the total number of patients in each arm for whom an order was pended and the alert fired.

TUTS referral rate is defined as the number of patients for whom a referral to Penn Medicine’s Smoking Cessation Program was placed in the inpatient setting divided by the total number of patients in each arm for whom an order was pended and the alert fired.

These measures will be collected only from patients referred to [name] program for treatment:

Quit Line rate, defined as the total number of patients who present for quit line counseling (i.e. telephone or electronic), divided by the total number of patients referred to the Smoking Cessation Program

Medication recommendation rate, defined as the total number of patients who are recommended to receive a tobacco use treatment medication by the TUT Service staff in quit line counseling divided by the total number of patients who present for quit line counseling

Follow-up recommendation rate, defined as the total number of patients who are recommended to receive a tobacco use treatment medication or a follow-up appointment by the TUT Service staff in quit line counseling divided by the total number of patients who present for quit line counseling

Proposed survey measures, including ease and appropriateness, are noted in the attached survey form and will be submitted to the IRB for review prior to survey launch.

5 Study Procedures

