2.1 Primary Objectives

The objective of this study is to examine a novel approach to improving the quality of care inpatients receive if they use tobacco (oncology and general inpatients).

Specific Aim 1: *Assess whether including a standing order for prescription and management of varenicline (TUT Service+VM) within the inpatient clinical workflow for cancer and non-cancer patients identified as current smokers will significantly increase TUT engagement rates compared to current standard of care (TUT Service alone). Hypothesis:* Observed treatment engagement rates will be higher among clinicians exposed to TUT Service+VM than observed in clinicians exposed to TUT Service alone.

Specific Aim 2: *Assess whether clinicians exposed to the TUT Service+VM condition will be more effective at guiding reluctant patients toward TUT engagement than clinicians exposed to the TUT Service alone condition. Hypothesis:* Rates of important TUT behaviors (e.g. treatment initiation, quit attempts, and others) observed among smoking patients of clinicians exposed to TUT Service+VM will be higher than those than observed among smoking patients of clinicians exposed to TUT Service alone.

Specific Aim 3: *Assess implementation preferences and barriers influencing effectiveness of usual care tobacco use treatment (TUT Service) + varenicline management (VM) applied within the cancer center. Hypothesis:* Oncology specialists exposed to the TUT Service + VM condition will identify key facilitators and barriers to the implementation of the TUT Service + VM condition that can help guide subsequent dissemination efforts.

The goal of this study is to determine if the default for a varenicline order increases clinician referral to TUTS and/or the treatment of tobacco use. At this point, many clinicians are turning the referral order off and patients are not receiving treatment for tobacco use. A default to prescribe treatment may help override barriers to both. While we are focused on cancer inpatients, we will assess the impact of the varenicline management intervention on cancer and non-cancer patients.

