5.2 Novel BE intervention

Our VM intervention builds upon the established TUT Service process. In addition to connecting the patient to TUT Service via electronic referral, it activates a medication management protocol that: 1) actively confirms no evidence of renal failure or pregnancy with the provider, 2) automates a referral to prescribing providers within the TUT Service team, prompting a call-back to patient within 24 hours, 3) provides written AVS instructions to contact TUT Service for initiation instructions and clinic appointment, and 4) pends a varenicline prescription to the medication list, ready for reconciliation by TUT Service prescribing clinicians. The protocol formalizes standard management principles for varenicline, including follow-up evaluation, pre-quit period duration, and side effect amelioration.(52)

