5.3 Varenicline Management

The Research intervention in this protocol is best described as a two-step procedure for transferring responsibility for tobacco dependence medication management and follow-up to a recognized consulting clinical service. The steps: 1) Upon executing the order for "Varenicline Management Protocol" in the patient's electronic record, the subject clinician automatically sends an electronic alert the Tobacco Use Treatment team, indicating their desire to begin varenicline pharmacotherapy as part of the patient's cancer care; 2) A prescribing provider within the tobacco use treatment team initiates standard clinical care of the patient within 24 hours of the order, focused on initiating pharmacotherapy of tobacco dependence using current evidence-based guidelines of care.

As background, recognize that "standard clinical care of the patient" in this context includes:

- i) contacting the patient to ascertain suitability for varenicline therapy, including history of prior use, insurance coverage, etc.
- ii) ascertain the presence of any potential complications of varenicline use (i.e. current pregnancy, uncontrolled seizure disorder) or necessary dose adjustments (i.e. reduced creatinine clearance)
- iii) educate patient regarding proper use and anticipated effects of varenicline, including proper dosing, schedule, possible side effects, and available alternatives.
- iv) providing patient with written information regarding the medication
- v) arrange for an outpatient visit in clinic to follow-up, provide dependence counseling, and make medication adjustments as needed.

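### Two of the three downstream rates in Section 4.2 count recommendations by TUT Service staff, whose work the VM protocol directs, not the patient behaviours that Aim 2 names

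*Combined protocol and SAP*

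**What the plan says.** **Aim 2.** Section 2.1 states the hypothesis in terms of what patients do: "Rates of important TUT behaviors (e.g. treatment initiation, quit attempts, and others) observed among smoking patients" are expected to be higher when the clinician is in the VM arm.

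**Defined rates.** Section 4.2 defines three rates collected only from referred patients:

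1. Quit Line rate. The numerator is "the total number of patients who present for quit line counseling (i.e. telephone or electronic"). The denominator is every patient whom the clinicians referred to the programme.
2. Medication recommendation rate. The numerator is patients "recommended to receive a tobacco use treatment medication by the TUT Service staff in quit line counseling"; the denominator is patients who present for that counselling.
3. Follow-up recommendation rate. The numerator is patients "recommended to receive a tobacco use treatment medication or a follow-up appointment by the TUT Service staff" during that counselling; the denominator is the same as for rate 2.

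**VM arm.** Section 5.2 says the VM order "automates a referral to prescribing providers within the TUT Service team, prompting a call-back to patient within 24 hours", and that it pends a varenicline prescription for the service's prescribers. Section 5.3 describes the resulting care as "focused on initiating pharmacotherapy of tobacco dependence using current evidence-based guidelines of care" and lists among its elements to "arrange for an outpatient visit in clinic to follow-up, provide dependence counseling, and make medication adjustments as needed".

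**Usual care.** Section 5.1 has counsellors assess the patient and form a recommendation around that patient's priorities, with the aim of moving the patient on to continuing services. It mentions no timed call-back, pended prescription or arranged visit.

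**Data and analysis.** Section 3 says that use of cessation treatments and quit attempts are recorded as standard clinical information for referred patients. Section 5.5 says Aim 2 relies on self-reported measures of effect. Section 6.2 specifies a chi-square comparison of rates for Aims 1 and 2 without listing which rates belong to which aim.

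**The concern.** An outcome for Aim 2 should show that patients behaved differently because of what the randomised clinician was shown. Rates 2 and 3 do not do that directly. The act they count is performed by the TUT Service, which is neither the patient nor the randomised clinician. In one arm only, a protocol tells that service to do closely matching things. The staff also know when a VM order has been placed, because under Section 5.3 the order alerts them.

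A significant chi-square on either rate could then be reported as support for Aim 2 when it reflects how the service was instructed to work. The behaviours that would settle the question, treatment initiation and quit attempts, are named in the hypothesis but have no numerator or denominator in Section 4.2.

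**Working it through.** The plan states no expected rate, effect size or sample size for Aim 2, so there is no figure to reproduce. The check compares definitions, followed by an illustration on assumed rates.

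**Step 1: who performs the counted act?**

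| Rate (4.2) | Counted act | Who acts | Matching VM step (5.2, 5.3) | Usual care (5.1) |
|---|---|---|---|---|
| Quit Line | Presenting for counselling | Patient | Call-back within 24 hours; not stated whether answering it counts | No call-back described |
| Medication recommendation | Recommending any cessation medication | TUT Service staff | Care aimed at starting pharmacotherapy; varenicline pended | Individualised recommendation |
| Follow-up recommendation | Recommending medication or an appointment | TUT Service staff | As above, plus arranging a visit | Individualised recommendation; aim of continuing services |

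The overlap is direct for the two recommendation rates and conditional for the Quit Line rate.

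**Step 2: are rates 2 and 3 separate evidence?** Anyone counted in rate 2 is also counted in rate 3, over the same denominator. Rate 3 is therefore never below rate 2, and agreement between them is partly built in.

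**Step 3: what could happen with identical patient behaviour?** All rates here are assumptions. Let p_C be the control recommendation rate and f the share of presenting VM patients, otherwise without a recommendation, for whom the VM script adds one. Then

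p_V = p_C + f(1 − p_C).

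With n presenting patients per arm, treated as independent, the chance of a significant two-sided 5% chi-square is about

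Φ{[(p_V − p_C)√n − 1.96√(2p̄(1 − p̄))] / √[p_C(1 − p_C) + p_V(1 − p_V)]}, where p̄ is the mean of the two rates.

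Example: p_C = 0.60 and f = 0.5 give p_V = 0.60 + 0.5 × 0.40 = 0.80. With n = 100 this is Φ[(0.20 × 10 − 1.96√0.42)/√0.40] = Φ(1.15), or about 88%.

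| p_C | f | p_V | Chance, n = 100 per arm |
|---|---|---|---|
| 0.40 | 0.25 | 0.55 | 57% |
| 0.60 | 0.25 | 0.70 | 32% |
| 0.80 | 0.25 | 0.85 | 15% |
| 0.40 | 0.50 | 0.70 | 99% |
| 0.60 | 0.50 | 0.80 | 88% |
| 0.80 | 0.50 | 0.90 | 51% |

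If f = 0 there is no built-in difference. If p_C is already 0.90, the largest possible gap is 1.00 − 0.90 = 10 points. Clinicians, not patients, are randomised, so the independence assumption is a simplification.

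**Step 4: Quit Line rate.** If the call-back is not counted as presenting, it adds nothing by definition. If it is counted and converts an assumed 20% of non-presenters, control rates of 10%, 30% and 50% become 28%, 44% and 60% (for example 0.30 + 0.20 × 0.70 = 0.44). The chance of significance with 100 referred per arm is then 91%, 54% and 29%.

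**Step 5: direction.** The denominators (referred, presenting) form after randomisation. Take 100 alerts per arm and the 60% and 80% referral levels of Section 6.1. Assume 50% of the first 60 referred patients present in either arm, and 10% of the extra 20 in the VM arm. Control is 30/60 = 50%. VM is (30 + 2)/80 = 40%. The Quit Line rate falls although more patients presented: 32 against 30 per 100 alerts. A VM advantage is therefore not guaranteed on these denominators.

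**The case against.** The strongest reply is that VM is a bundle. Transferring management to the TUT Service is part of what is being tested in a pragmatic pilot, so a change in what the service delivers is a legitimate effect. That stands, and it is why the recommendation rates are worth reporting. It does not make them evidence that a patient started treatment or tried to quit.

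The arms also differ less sharply than a quick reading suggests. Usual-care counsellors make recommendations too. Section 5.3 presents its list as background on standard care and includes checks on suitability and discussion of alternatives, so it does not require a recommendation for every patient. Nor is it stated that a VM prescriber's contact counts as quit line counselling, which rates 2 and 3 require. These points limit how far VM can move the rates; they do not remove the overlap.

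Section 4.2 does not label the three rates as Aim 2 outcomes. Assigning them to Aim 2 is an inference, though a fair one: they are the only defined rates downstream of the hospital orders and referral. If they are not Aim 2 outcomes, Aim 2 has no defined patient-behaviour outcome at all.

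A reader might infer that all three rates simply record VM steps. The documents do not support that: the Quit Line rate needs the patient to take part, and its overlap with the call-back is possible but not established. Nor does any of the three record drug initiation; rate 2 counts a recommendation of any cessation medication.

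**Conclusion.** The point holds for the medication and follow-up recommendation rates. They count staff acts, the VM protocol steers that staff in one arm, and a difference can arise with no change in the behaviours Aim 2 names, for which Section 4.2 defines no rate. The two rates are nested and should not be read as two findings. The Quit Line rate is open to the same problem only if an answered call-back counts as presenting, which the plan leaves undefined.

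The size and direction of any built-in difference cannot be derived from the documents. Under the assumed rates above, the chance of a significant result with no patient acting differently runs from 15% to 99% with 100 presenting patients per arm, and there is no built-in gap if the script adds no recommendations. A reader might infer a fixed built-in gap in favour of VM, or that a significant difference would show nothing beyond adherence to the protocol. Neither follows: control rates are not given, the post-randomisation denominators can move a rate either way, and a difference could also contain a real effect.

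The primary measure, engagement in Section 6.1, is unaffected. This is a correction the sponsor should make to Aim 2, not a flaw in the whole trial.

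**What to change.** In Sections 4.2 and 6.2:

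- Report the medication and follow-up recommendation rates as process measures, and do not test them as Aim 2 outcomes.
- Define presenting for quit line counselling by one rule for both arms. The VM call-back alone should not count.
- Base Aim 2 on behaviours that Section 3 says are already recorded clinically (use of cessation treatment, quit attempts) and on completed counselling sessions. The denominator should be all patients whose alert fired, as Section 4.2 already uses for the ordering rates.
- Count patients who were not referred, or who have no programme record, as not having the event, and state this as a limitation.

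The cost is mainly wording, plus defining and extracting these items from existing EHR and programme records. The downsides are lower absolute rates, probably fewer favourable secondary results, and under-capture of behaviour outside the programme. If VM raises referral, that under-capture may be smaller in the VM arm. The rates should therefore be described as behaviour documented through the service and read alongside the referral rate.

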5.1 Usual Care (control condition)

The TUT Service utilizes the Ask, Advise, and Connect referral framework.(28) This approach utilizes CDS logic embedded within the new patient intake routines. Standardized mandatory assessment of smoking status for all oncology patients automatically integrating cancer-relevant cessation advice in the written After Visit Summary (AVS), and sends an electronic referral to Certified Tobacco Treatment Specialists (CTTS) trained in the unique counseling requirements of patients.(51) Counselors assess the patient's educational, emotional, interpersonal, and skill-based needs, and develop a treatment recommendation based on the patient's priorities. The goal is to direct the patient to ongoing clinical services, either in a face-to-face setting or via telephone/digital quit line support.

5.2 Novel BE intervention

Our VM intervention builds upon the established TUT Service process. In addition to connecting the patient to TUT Service via electronic referral, it activates a medication management protocol that: 1) actively confirms no evidence of renal failure or pregnancy with the provider, 2) automates a referral to prescribing providers within the TUT Service team, prompting a call-back to patient within 24 hours, 3) provides written AVS instructions to contact TUT Service for initiation instructions and clinic appointment, and 4) pends a varenicline prescription to the medication list, ready for reconciliation by TUT Service prescribing clinicians. The protocol formalizes standard management principles for varenicline, including follow-up evaluation, pre-quit period duration, and side effect amelioration.(52)

5.3 Varenicline Management

The Research intervention in this protocol is best described as a two-step procedure for transferring responsibility for tobacco dependence medication management and follow-up to a recognized consulting clinical service. The steps: 1) Upon executing the order for "Varenicline Management Protocol" in the patient's electronic record, the subject clinician automatically sends an electronic alert the Tobacco Use Treatment team, indicating their desire to begin varenicline pharmacotherapy as part of the patient's cancer care; 2) A prescribing provider within the tobacco use treatment team initiates standard clinical care of the patient within 24 hours of the order, focused on initiating pharmacotherapy of tobacco dependence using current evidence-based guidelines of care.

As background, recognize that "standard clinical care of the patient" in this context includes:

- i) contacting the patient to ascertain suitability for varenicline therapy, including history of prior use, insurance coverage, etc.
- ii) ascertain the presence of any potential complications of varenicline use (i.e. current pregnancy, uncontrolled seizure disorder) or necessary dose adjustments (i.e. reduced creatinine clearance)
- iii) educate patient regarding proper use and anticipated effects of varenicline, including proper dosing, schedule, possible side effects, and available alternatives.
- iv) providing patient with written information regarding the medication
- v) arrange for an outpatient visit in clinic to follow-up, provide dependence counseling, and make medication adjustments as needed.

5.4 Inclusion of Non-cancer Patients

After testing the logic of the usual care intervention and the Novel BE intervention, it was determined that these two groups were being treated differently. In the usual care intervention, clinicians would receive the standard TUT Service BPA for all patients, regardless of cancer status. However, in the Novel BE intervention, the clinicians would receive the TUTS + VM BPA for their patients with a cancer history but would also be exposed to the standard TUT Service BPA for their patients without a cancer history. To ensure that these two groups are experiencing the same treatment, we are altering the study logic so that the clinicians randomized to the study Novel BE intervention will be exposed to the TUTS + VM BPA regardless of a patient's cancer status. This will also allow us to test the effect of the intervention on all inpatients, on non-cancer in-patients, and on just cancer inpatients. This change simplifies the system and expands our ability to test the impact of the intervention on differing in-patient populations.

5.5 Data Collection

All clinicians and sites use EpicCare (Epic Systems Corporation, Verona, WI) to deliver care. Penn Medicine Information Systems (IS) - [name], Penn EPIC Research Team - oversees successful integration of TUT Service CDS into ACC workflow. [name] generates quarterly reports and delivers them electronically to the TUT Service managers ([name], and [name]). Aim 1 & 2 data is of high quality; each report is assessed for quality and accuracy through review of the primary medical record in a random subset of instances. Aim 2 utilizes self-reported measures of effect, derived from in-person clinical (CTTS) contact, providing multiple opportunities to confirm the accuracy of self-reported status. Our experience to date suggests that these measures are highly reliable global metrics. To protect subject privacy, clinician decision-making and patient health record security is stronger than with most other web-based utilities. Numerous layers of data security ensure confidentiality. Data Transfer is exclusively via SSL encryption, protecting data transfer between staff. This is the same technology that is used to protect consumer information (e.g., credit cards) from interception in transit over the Internet. All research data is stored in a secure Oracle database housed behind secure health system firewall.

5.6 Administration of Surveys and/or Process

Clinicians will be invited to complete a survey in the fall of 2023. We anticipate that this survey will take no more than 10 minutes to complete. The survey will measure clinician characteristics, opinions and experiences using the best practice alerts from the study, and related cognitive biases. We will keep the number of items as low as possible to reduce clinician fatigue and increase response rates. Please see the attached survey form for more detail.

Survey data will be collected through REDCap (a secure, web-based application for collecting and managing survey data that can be completed via computer or mobile device). Clinicians from the initial pilot (Aims 1-2) will be sent a link to the REDCap form via email. If a clinician clicks the link to learn more about participating, they will be routed to a webpage within REDCap that outlines all required consent elements. If they decide to participate, they will click a button which will route them to the first page of the survey. Clicking this button indicates their agreement to participate in this aim of the study. See the **Informed Consent** section for more details regarding this process.

